7.3	SUBJECT POPULATION(S) FOR ANALYSIS	34
8	SAFETY AND ADVERSE EVENTS	34
8.1	DEFINITIONS	34
8.2	RECORDING OF ADVERSE EVENTS	38
8.3	REPORTING OF SERIOUS ADVERSE EVENTS AND UNANTICIPATED PROBLEMS	38
8.3.1	Sponsor-Investigator reporting: notifying the Mayo IRB	39
8.3.2	Sponsor-Investigator reporting: Notifying the FDA	41
8.4	UNMASKING/UNBLINDING PROCEDURES	42
8.5	STOPPING RULES	42
8.6	MEDICAL MONITORING	43
8.6.1	Internal Data and Safety Monitoring Board	44
9	DATA HANDLING AND RECORD KEEPING	45
9.1	CONFIDENTIALITY	45
9.2	SOURCE DOCUMENTS	45
9.3	CASE REPORT FORMS	45
9.4	RECORDS RETENTION	48
10	STUDY MONITORING, AUDITING, AND INSPECTING	49
10.1	STUDY MONITORING PLAN	49
10.2	AUDITING AND INSPECTING	58
11	ETHICAL CONSIDERATIONS	58
12	STUDY FINANCES	58
12.1	FUNDING SOURCE	58
12.2	CONFLICT OF INTEREST	59
12.3	SUBJECT STIPENDS OR PAYMENTS	59
13	PUBLICATION PLAN	59
14	REFERENCES	59

List of Abbreviations

LIST OF ABBREVIATIONS

AE	Adverse Event/Adverse Experience
CFR	Code of Federal Regulations
CRF	Case Report Form
DSMB	Data and Safety Monitoring Board
FDA	Food and Drug Administration
GCP	Good Clinical Practice
HIPAA	Health Insurance Portability and Accountability Act
IB	Investigator's Brochure
IND	Investigational New Drug Application
IRB	Institutional Review Board
PHI	Protected Health Information
PI	Principal Investigator
SAE	Serious Adverse Event/Serious Adverse Experience
SOP	Standard Operating Procedure

Study Summary

Title	Effects of Niacin on Intramyocellular Fatty Acid Trafficking in Subjects with Upper Body Obesity and Type 2 Diabetes Mellitus
Running Title	Effects of niacin on FFA in UBO and T2DM in insulin resistant states
Protocol Number	17-009977
Phase	Pilot Study
Methodology	Randomized, placebo-controlled; cross-over design
Overall Study Duration	2 years
Subject Participation Duration	6-8 weeks
Single or Multi-Site	Single site
Objectives	Evaluate the effect of niacin or placebo on intramyocellular fatty acid trafficking in subjects with upper body obesity and type 2 diabetes mellitus
Number of Subjects	10 upper body obese and 10 Type 2 diabetic participants will be recruited for this study for a total of 20 participants between the ages of 18-65 years.
Diagnosis and Main Inclusion Criteria	Individuals with upper body obesity and Type 2 diabetics will be included in the study.
Study Product, Dose, Route, Regimen	Niacin (nicotinic acid). Dose: 0.6 mg/minute - 2.8 mg/min for 12 hours. Dose route: intravenous Dose regime: ~ 1.4 mg/min for 12 hours
Duration of Administration	17 hours on one occasion

Reference therapy	The volunteers will undergo a separate study where they will receive intravenous saline without niacin
Statistical Methodology	The incorporation of plasma free fatty acids into intramyocellular lipids will be compared between the saline control day and the niacin infusion day (paired t-test). We will assess whether the incorporation of plasma fatty acids into intramyocellular lipids is related to insulin sensitivity measured by a euglycemic, hyperinsulinemic clamp using linear regression approaches. We will also assess whether the incorporation of plasma fatty acids into intramyocellular lipids is correlated with the activation of the insulin signaling cascade (Western blotting) in muscle using linear regression approaches.

1 Introduction

This document is a protocol for a human research study. This study will be carried out in accordance with the applicable United States government regulations and Mayo Clinic research policies and procedures.

1.1 Background

Under normal circumstances adipose tissue is extremely insulin sensitive. Insulin inhibits adipose tissue lipolysis and thereby causes a rapid decrease in plasma free fatty acid concentrations. This insulin-mediated inhibition of lipolysis is impaired in upper body obese compared to lower body obese and normal weight adults (1-3). Humans with type 2 diabetes mellitus (T2DM) have an even more pronounced insulin resistance with regards to lipolysis (4, 5). This insulin resistance results in over-exposure of muscle to free fatty acids (FFA), which can cause insulin resistance in muscle. Thus, it is unsurprising that adults with upper body/visceral obesity (UBO) and Type 2 Diabetes are typically more insulin resistant with respect to glucose metabolism than those with lower body obesity (LBO).

These excess FFA can cause insulin resistance by interfering with insulin signaling. Increased FFA concentration and flux is thought to be a major contributor to insulin resistance in muscle (6) and to stimulate hepatic gluconeogenesis (7). Although insulin resistance is conventionally defined in terms of insulin's effects on glucose metabolism, it is clear that insulin resistance is also present at the level of the adipocyte, with marked resistance to the antilipolytic effects of insulin in obesity (2) and T2DM (8, 9).

Despite a large number of studies of how FFA contribute to health and disease (10-26), we and others (27) contend that the mechanisms by which fatty acids affect muscle insulin resistance remains to be fully delineated. The extent to which observed differences in muscle insulin action are the result of altered delivery (elevated adipose tissue lipolysis/FFA concentrations) or altered intramyocellular FFA trafficking into lipotoxic intermediates has not been studied in an integrated fashion. We propose to address these questions by comprehensively assessing muscle fatty acid metabolism in humans with varying degrees of pre-existing and experimentally altered insulin sensitivity. By determining the mechanisms by which elevated plasma FFA

concentrations and differences in intramyocellular trafficking, we will gain a better understanding of insulin resistance and therefore potential therapies for insulin resistance and T2DM.

We therefore propose to address the following questions: 1) Do UBO and T2DM differ with respect to muscle FFA uptake and muscle fatty acid trafficking (i.e. are lipotoxic intermediates from FFA greater in T2DM than UBO relative to muscle FFA exposure) 2) Will overnight, sustained suppression of FFA in UBO and T2DM improve insulin action with respect to glucose metabolism; 3) If so, will this be statistically related to the contribution of FFA to intramyocellular diacylglycerols (DG) and/or ceramides?

Hypothesis: Compared to a saline control experiment, overnight suppression of FFA with intravenous niacin will decrease trafficking of plasma FFA into intramyocellular ceramides and/or DG and will improve insulin signaling and insulin-stimulated glucose disposal.

Rationale: Niacin at high doses suppresses adipose tissue lipolysis via the PUMA-G receptor, independent of insulin. Suppression of FFA with Acipimox (a lipid-lowering niacin derivative) improved muscle insulin sensitivity with regards to glucose metabolism and Akt phosphorylation (66). Surprisingly, this was not accompanied by reductions in whole muscle ceramide or DG concentrations. While it is possible that neither DG nor ceramides were responsible for the abnormal insulin signaling (66), it is also possible that specific DG or ceramide species or the subcellular localization of those species, which were not measured by Liang et al (66), accounted for the improved insulin signaling/action.

1.2 Preclinical and clinical data

Niacin, as a lipid-lowering treatment, is given chronically (for years) and safely at doses of 3g/day. We have given niacin (as Niaspan[®]) 1 g orally each hour for two hours {Ali, 2015 #107} with no adverse events. Intravenous niacin has been a component of the standard vitamin cocktail for parenteral nutrition for several decades. The daily therapeutic parenteral requirement in adults is 40 mg per day {Bistrian, 2015 #106}. Nelson et al {Nelson, 2012 #18} administered niacin as an

intravenous infusion for two hours starting at 0.6mg/min and increasing to 2.8 mg/min over 30 min; the only observed effect was asymptomatic flushing. In our proposed study we will use a one-time dose that is less than the typical daily dose used for chronic treatment of hyperlipidemia. Given the safety of the route (intravenous) and the moderate dose (~1 gm over 12 hours), we anticipate this is a safe means to temporarily lower plasma FFA concentrations for the purposes of this NIH funded study.

The proposed studies will measure the relative contribution of plasma FFA to intramyocellular signaling molecules (DG and ceramides), as well as the incorporation into imTG and subsequent appearance in long-chain acylcarnitines in adults with a wide range of insulin sensitivity with respect to glucose metabolism. By integrating information regarding the concentrations of lipid signaling molecules, the contribution of plasma FFA to these molecules, and the insulin signaling pathway we will be able to determine the extent to which varying degrees of insulin resistance are due to altered intramyocellular fatty acid trafficking.

Suppression of FFA – an insulin sensitizing approach. Acipimox, a long-acting niacin analog, has been used to suppress FFA through a non-insulin mechanism (72) and thereby study the adverse effects of elevated FFA (66, 73-76). Seven days of Acipimox treatment improved insulin mediated stimulation of glucose disposal in T2DM, but not undifferentiated obese subjects (66). This treatment also increased insulin stimulated Akt phosphorylation in T2DM (66), but did not reduce the elevated whole muscle ceramide content in obese or T2DM and did not change muscle DG concentrations, which were not different between lean, obese and T2DM at baseline (66). Unfortunately, these authors could not document whether FFA were suppressed in a sustained manner, did not have measures of the DG and ceramides species, and measured only whole muscle content of these molecules. Furthermore, they did not characterize their non-diabetic obese volunteers with regards to fat distribution, which may explain why insulin-stimulated glucose disposal per kg fat free mass was equal to or greater in obese than lean controls. Our colleague, [name], has developed a protocol for intravenous niacin administration that suppresses FFA in a sustained manner (77); he has shared with us his protocol to facilitate the application for our own IND. By administering overnight intravenous niacin infusion we propose to test the hypothesis that lowering FFA in truly insulin resistant UBO and T2DM improves: 1) whole body

insulin sensitivity; 2) muscle insulin signaling; 3) subcellular (SS vs. IMF) content of DG and ceramides; 4) the contribution of plasma FFA to these molecules.

In this study we propose to assess the subcellular location of DG and ceramides to better understand their relationship to altered insulin signaling. We will also test the hypothesis that sustained suppression of FFA alone can alter the trafficking of FFA into less “toxic” metabolites and thereby improve insulin action.

1.3 Investigational Agent

Name of product: Nicotinic acid

Brief description: Niacin will be received by Research Pharmacy in powder form. The drug will be administered intravenously by a Baxter infusion pump model Sigma Spectrum, after reconstitution by pharmacy.

1.4 Dose Rationale

Subjects will first receive a titrated dose starting from 0.6 mg/min to a maximum of 2.8 mg/min (likely needed dose = 1.4 mg/min) or 0.9% NaCl. We will collect blood samples overnight during the infusion to determine the lowest possible dose of niacin needed to suppress plasma FFA concentrations to those observed in overnight, postabsorptive, lean, healthy adults. The infusion rate will be titrated to a maximum of 2.8 mg/min only if lower doses do not result in the needed reductions in plasma FFA. The dose of 2.8 mg/min has been shown to result in sustained suppression of plasma FFA concentrations (a reflection of adipose tissue lipolysis) to much lower levels than are needed for the purposes of this study {Nelson, 2012 #18}. Therefore, we anticipate considerably lower niacin doses will be needed. The gradual dose escalation and a pre-study dose of 325 mg of aspirin will prevent or minimize the side effects of flushing due to niacin.

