The change in the ratio of phosphorylated to total insulin signaling effector proteins between the first and second muscle biopsy will be used to assess the insulin-mediated activation of insulin signaling pathways. We will assess insulin signaling in biopsies taken under basal and insulin stimulated conditions at the level of Akt phosphorylation using capillary Western blot approaches to quantify phosphorylation (80). Glucose disappearance rates under euglycemic, hyperinsulinemic conditions are an excellent reflection of muscle glucose uptake, and this will be

used as our index of muscle glucose disposal. Indirect calorimetry will be done prior to the first and second muscle biopsies to provide context for substrate utilization and energy expenditure. We will perform abdominal subcutaneous adipose tissue biopsies in order to measure fat cell size and the inflammatory characteristics of adipose tissue because these factors have been related to insulin resistance in muscle. The biopsies will be done using sterile technique under local anesthesia and will be done on different sides of the abdomen.

[figure not shown]

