5.3 Method for Assigning Subjects to Treatment Groups

Subjects will first receive niacin and for the second study they will receive intravenous saline as the placebo.

Preparation and Administration of Study Drug

Nicotinic acid will be received in powder form and compounded at Research Pharmacy following Compounding Procedures and an approved compounding formula sheet, for intravenous administration which runs in a Baxter infusion pump model Sigma Spectrum. The drug will be aliquoted in single dose amber vials of 10 mL each and refrigerated at a temperature of 2-8°C.

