5.5 Prior and Concomitant Therapy

The following medications will be withheld 3 days prior to beginning of the study:

- Participants with Type 2 Diabetes on insulin will have their long-acting insulin replaced with a short-acting insulin.

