6.2 Visit 1 (In-patient visit, 1 night stay)

At visit 1 the subjects will undergo the following:

- Admission to in-patient facility the evening prior to scheduled biopsies
- Negative urine pregnancy test (for females of childbearing potential only) 48 hours prior to dosing.
- Vital signs (blood pressure, pulse rate, respiratory rate, and body temperature)
- Body weight
- Concomitant and non-drug therapies
- Niacin or saline infusion started the evening prior

Volunteers will be asked to stop taking any aspirin or ibuprofen from three days before to three days after their overnight stays.

All participants will consume an isoenergetic diet (weight stable, 45% carbohydrate, 20% protein and 35% fat) from the Mayo Clinical Research and Trials Unit (CRTU) for 1-3 days prior to the niacin infusion study and 3 days before the saline control study. This will assure consistency of energy intake and nutrient composition prior to the study saline control study that is helpful in reducing variability in plasma FFA concentrations.

Following admission to the CRU the evening prior to the studies a forearm intravenous catheter will be placed for infusion of niacin, insulin, glucose and isotopic tracers. T2DM volunteers taking insulin will be asked to withhold their long-acting insulin for 3 days prior to the study, manage their blood sugar with short acting insulin, and receive an overnight, monitored infusion of regular insulin to maintain blood glucose values between 4.5-5.5 mmol/L. At 2100 h the infusion of intravenous niacin (or saline) will begin. The initial niacin dose will be 0.6 mg/min and, depending upon symptoms, the rate increased by 0.4 mg/min increments to a goal of 1.4 mg/min. A retrograde intravenous catheter will be placed to allow for blood sampling at 2200 h, 2400 h, 0200 and 0400 h. The niacin/saline infusion will be continued until 0900 h the following morning. The niacin infusion will be weaned off gradually in order to prevent a rebound increase in plasma FFA. Depending upon the degree of overnight suppression of FFA concentrations, the dose may be adjusted downwards or upwards in subsequent studies to a maximum of 2.8 mg/min in subsequent studies. At 0400 h an infusion of $[U-^{13}C]palmitate$ (330 nmol/min) will be initiated to trace FFA contribution to intramyocellular lipids in the euinsulinemic state (13,15). At 0600 h an infusion of $[6-^2H_2]glucose$ will be started to trace glucose metabolism and continued till the

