6.3 Visit 2 (In-patient visit, 1 night stay)

After ~4 weeks subjects will return to the CRTU and the same procedure and guidelines as Visit 1 will be repeated with the saline/placebo.

7 Statistical Plan

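### Sections 1.4 and 6.2 are not reconciled on aspirin, and the protocol does not say whether aspirin exposure is the same on the niacin and saline days

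*Combined protocol and SAP*

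**What the plan says.** Two sections mention aspirin.

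- Section 1.4 (Dose Rationale) says that, together with gradual escalation of the infusion, "a pre-study dose of 325 mg of aspirin will prevent or minimize the side effects of flushing due to niacin". It gives no clock time, no visit and no one responsible for giving the dose.
- Section 6.2 (Visit 1) says: "Volunteers will be asked to stop taking any aspirin or ibuprofen from three days before to three days after their overnight stays". The plural covers both inpatient visits. No reason and no exception are given.

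The surrounding text fixes the setting. On the evening of admission, "At 2100 h the infusion of intravenous niacin (or saline) will begin". The order is the same for everyone (section 5.3): "Subjects will first receive niacin and for the second study they will receive intravenous saline as the placebo". At Visit 2 (section 6.3), "the same procedure and guidelines as Visit 1 will be repeated with the saline/placebo". The Study Summary makes the main analysis a within-person contrast: incorporation of plasma free fatty acids (FFA) into intramyocellular lipids "will be compared between the saline control day and the niacin infusion day (paired t-test").

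Section 5.5, where a concomitant aspirin rule would be expected, opens with "The following medications will be withheld 3 days prior to beginning of the study" and lists only the replacement of long-acting insulin.

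**The concern.** One section counts on an aspirin dose before niacin. Another asks for no aspirin around the same stay, and nothing links the two. Two things are at stake.

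**Conduct and safety.** Muscle and adipose biopsies are scheduled at both stays, and section 1.5 lists haematoma and bruising among their risks. Staff should not have to infer whether aspirin is expected or excluded beforehand. Section 8.2 also says that biopsy bruising will not be reported as an adverse event, so a difference in bruising between the two days could pass unseen. Section 3.6 makes symptoms during the niacin infusion the primary safety endpoint, and those symptoms cannot be read properly without knowing whether the stated flushing measure was used.

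**Interpretation.** Section 1.2 sets out to test what sustained FFA suppression does on its own. If aspirin accompanies niacin but not saline, the paired difference no longer isolates niacin. Among the measurements is "the inflammatory characteristics of adipose tissue" (section 3.1), although this is not a primary or secondary endpoint in sections 3.4 and 3.5.

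**Working it through.** The plan gives no figure to reproduce here. The check is a comparison of the text, followed by simple bookkeeping on the paired difference.

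**1. Timing.** The infusion starts at 2100 h. Baseline samples run to 0900 h and the first biopsies follow, about 12 hours after the start. The clamp begins at 0915 h (section 3.1) and lasts 5 hours, so the second biopsies come at about 1415 h, or 17 h 15 min after the start. Assume that the pre-study dose is taken on the admission evening, before 2100 h. It then falls inside the no-aspirin window and precedes both sets of biopsies. The protocol does not state the time of the dose, so this is an assumption based on its purpose.

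**2. Is the conflict resolved elsewhere?** Aspirin does not appear in:

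- the risks (1.5)
- the treatment regimen (5.2)
- prior and concomitant therapy (5.5)
- the Schedule of Events (section 6)
- the list of Visit 1 procedures (6.2)
- Visit 2 (6.3)
- the text on managing flushing (10.1)

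**3. What section 6.3 settles.** Repeating Visit 1 with saline could mean aspirin on both days, if the section 1.4 dose counts as part of Visit 1. It could mean aspirin on neither day, because the Visit 1 procedures omit it. If aspirin is seen as part of the niacin regimen, it could mean the niacin day only. The wording does not choose between these.

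**4. Effect on the paired difference.** Let ν be the niacin effect, α the aspirin effect and π the Visit 1 minus Visit 2 effect, which is always present because the order is fixed. Assume that the effects add. If a fraction p of the 20 participants have aspirin on the niacin day only, and the rest have the same exposure on both days, the expected mean difference is ν + pα + π.

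| Aspirin exposure | p | Expected niacin minus saline |
|---|---|---|
| Neither day | 0 | ν + π |
| Both days | 0 | ν + π (niacin effect in the presence of aspirin) |
| Niacin day only, some participants | between 0 and 1 | ν + pα + π; p unknown unless recorded |
| Niacin day only, all 20 | 1 | ν + α + π |

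In the last row the aspirin indicator equals the niacin indicator on all 20 × 2 = 40 study days. No covariate or model can then separate α from ν. The bias on account of aspirin therefore runs from 0 to α. The documents give no value for α on any endpoint.

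**5. A second route.** Sections 3.1 and 6.2 let symptoms govern how far the niacin rate is raised. If aspirin reduces flushing, as section 1.4 asserts, uneven use could also change the niacin rate that participants reach. The documents give no figure for this either.

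**The case against.** The best reply is that the two sentences can coexist. Section 6.2 is worded as a request to volunteers and can be read as covering their own use at home and around the stay. A single study-supplied dose would then be an unstated exception. Section 1.4 is a rationale section, not an order, and may be a leftover: section 10.1 handles flushing with reassurance and hydration and does not mention aspirin.

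Much of this stands. A reader might infer that the two rules are strictly incompatible, and the text does not go that far. But section 6.2 covers all aspirin and states no exception. The harmonious reading has to be supplied by the reader, and it would still leave the saline day unspecified.

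A reader might also infer that aspirin is, as written, a co-intervention on the niacin day alone, present on 20 niacin days and 0 saline days. The documents do not establish that. It needs two steps that they leave open: that aspirin is actually given, and that it is not given at Visit 2. If section 6.2 governs, there is no aspirin confounding at all.

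Finally, no passage says why aspirin is to be stopped, or that one dose affects palmitate incorporation, insulin signalling, glucose disposal or biopsy bleeding. An effect on the primary endpoint is therefore possible but not shown.

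**Conclusion.** The point holds as an unreconciled instruction on a drug given or withheld around biopsies, together with silence on whether exposure is equal at the two visits. That part rests on the current text alone.

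The confounding is conditional. If aspirin is given, and only with niacin as its purpose in section 1.4 suggests, it is completely aliased with niacin in the paired comparison for all 20 participants, and this cannot be repaired in the analysis. If exposure is the same on both days, aspirin drops out of the difference under additivity. The size of any aspirin effect cannot be derived from the documents, so no claim is made that the primary result would be materially biased. Nor is any view taken here on which section is clinically right.

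The correction is worth making because it costs almost nothing before the visits and is not recoverable afterwards.

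**What to change.** 1. Reconcile sections 1.4 and 6.2 into a single aspirin instruction. The clinical choice is the sponsor's. If a study dose is intended, section 6.2 should state the exception; if not, section 1.4 should no longer rely on it.
2. State in sections 6.2 and 6.3 whether the instruction applies identically at the niacin and saline visits, and carry it into section 5.5 and the Schedule of Events.
3. Record aspirin exposure at both visits, covering any study dose and the volunteer's own use. The Schedule of Events marks medication reconciliation at screening only. Section 6.2 lists concomitant therapies at Visit 1 but does not provide for a study-given aspirin dose.
4. If exposure differs between visits, describe the contrast throughout as niacin plus aspirin versus saline, and do not attribute it to niacin or to FFA suppression alone.

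The cost is protocol wording and one recorded item at each visit, with no added participants or procedures.
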